| SLE | Systemic Lupus Erythematosus |
| TNF | Tumor Necrosis Factor |
| TNFR1 | TNF- α receptor |
| UM | University of Miami |
| VEGF | Vascular endothelial growth factor |

Protocol Synopsis

| | |
|--|--|
| Sponsor: ISCI / University of Miami Miller School of Medicine | |
| Name of Study Therapy: Allogeneic human Mesenchymal Stem Cells (hMSCs) | |
| Title of Study: A Phase I/II, Randomized, Double Blind, Pilot trial to evaluate the Safety and Efficacy of Allogeneic Mesenchymal Human Stem Cells infusion therapy for Endothelial DySfunctiOn in diabetic subjects. (ACESO Study) | |
| Study Center: ISCI / University of Miami Miller School of Medicine | Phase of Development: Phase I/II |
| 
Objectives:
 
Primary: To demonstrate the safety of allogeneic hMSCs administered via infusion therapy for diabetic subjects with endothelial dysfunction.
 
Secondary:
 
 -To determine the mechanisms underlying the endothelial effects of MSCs and whether targeting endothelial function via MSC therapy ameliorates Cardiovascular Disease (CVD) outcomes in subjects with diabetes mellitus. -To evaluate the dose and timing of the stimulatory effect of MSCs on circulating angiogenic factor levels and EPC function as well as FMD% within 28 days post-infusion. -To evaluate the long term effect of MSCs on circulating angiogenic factor levels and EPC function as well as FMD% at 3, 6, and 12 months post-infusion. | |
| 
Design and Investigational Plan:
 
To evaluate the role of allogeneic mesenchymal stem cells therapy for endothelial dysfunction in diabetes.
 
Sixteen (16) diabetic subjects with endothelial dysfunction will be scheduled to undergo a peripheral intravenous infusion after meeting all inclusion/exclusion criteria at baseline.
 
PILOT PHASE (Unblinded):
 
The dose for subjects in the pilot phase will vary from 20 million cells to 100 million cells and will be Unblinded, with subjects and study team members aware of the doses administered to the subject. The pilot phase will consist of:
 
Three (3) subjects will be treated with 20 million (20×10^6) allogeneic hMSC's Three (3) subjects will be treated with 100 million (100×10^6) allogeneic hMSC'
 
The three (3) subjects in the low dose group will not be treated less than 5 days apart and will each undergo full evaluation during those five days to show that there are no signs of treatment emergent SAE's (TE-SAE) before continuing with the treatment of further subjects.
 | |

The three (3) subjects in the high dose will not be treated until the three (3) subjects in the low dose have completed their one-month follow-up assessments and safety measures have been reviewed to confirm that there have been no treatment emergent SAE's. In addition, the three (3) subjects in the high dose group will not be treated less than 5 days apart.

Randomized Phase (Double-Blind):

After the pilot phase, subjects will be randomized to one of two treatments in a 1:1 fashion. This phase of the study will be blinded to both subjects and study team members. The randomized phase will consist of ten (10) diabetic subjects with endothelial dysfunction will be subsequently randomized to undergo a peripheral intravenous infusion after meeting all inclusion/exclusion criteria at baseline:

Five (5) subjects will be treated with 20 million (20×10^6) allogeneic hMSC's and Five (5) subjects will be treated with 100 million (100×10^6) allogeneic hMSC's

The Allo-hMSCs will be supplied from an allogeneic human mesenchymal stem cell source or commercial clinical grade bone marrow source manufactured by the University of Miami.

Follow up: Subjects will be followed at 3, 7, 14 and 28 days to evaluate the dose and timing of the stimulatory effect of MSCs on circulating angiogenic factor levels, EPC function, and FMD%, and at 3, 6, and 12 months post-infusion to complete all long-term safety and efficacy assessments.

Route of Administration: Peripheral Intravenous Infusion

Duration of Study participation: Approximately 12 months

Definition of Endpoints:

Safety (Primary): Incidence (at one-month post infusion) of any treatment-emergent serious adverse events (TE-SAEs), defined as the composite of: death, non-fatal pulmonary embolism, stroke, hospitalization for worsening dyspnea and clinically significant laboratory test abnormalities, determined per the Investigator's judgment.

Efficacy (Secondary): (Assess at Baseline, Day 3, 7, 14, 28, and Month 3, 6, and 12 following IV allogeneic MSC infusion)

1. Assess EPC-colony forming units (CFUs)
2. Assess circulating inflammatory markers (IL-1, IL-6, TNF α , and CRP)
3. Assess circulating angiogenic factors known to mobilize and recruit EPCs (VEGF, SDF-1 α , and SCF)
4. Assess FMD%

Major Inclusion Criteria:

- Be ≥ 21 and ≤ 90 years of age.
- Provide written informed consent.

- Have endothelial dysfunction defined by impaired flow-mediated vasodilation (FMD <7%).
- Have DM type 2 documented by hemoglobin A1C $\geq 7\%$ OR on medical therapy for diabetes.
- Females of childbearing potential must use two forms of birth control for the duration of the study. Female subjects must undergo a serum pregnancy test at screening and within 36 hours prior to infusion.

Major Exclusion Criteria:

- Be younger than 21 years or older than 90 years of age.
- Have a baseline glomerular filtration rate <35 ml/min $1.73m^2$ estimated using the MDRD formula.
- Have an ejection fraction $<45\%$ by gated blood pool scan, two-dimensional echocardiogram, cardiac MRI, cardiac CT or left ventriculogram within the past year, as documented by medical history.
- Have poorly controlled blood glucose levels with hemoglobin A1C $\geq 8.5\%$.
- Have a history of proliferative retinopathy or severe neuropathy requiring medical treatment.
- Have a hematologic abnormality as evidenced by hematocrit $< 25\%$, white blood cell $< 2,500/\mu l$ or platelet values $< 100,000/\mu l$ without another explanation.
- Have liver dysfunction, as evidenced by enzymes (AST and ALT) greater than three times the ULN.
- Have a bleeding diathesis or coagulopathy (INR > 1.3), cannot be withdrawn from anticoagulation therapy, or will refuse blood transfusions.
- Be an organ transplant recipient or have a history of organ or cell transplant rejection.
- Have a clinical history of malignancy within the past 5 years (i.e., subjects with prior malignancy must be disease free for 5 years), except curatively treated basal cell or squamous cell carcinoma, or cervical carcinoma.
- Have a condition that limits lifespan to < 1 year.
- Have a history of drug or alcohol abuse within the past 24 months.
- Be serum positive for HIV, Syphilis – VDRL (Confirmation with FTA-ABS if needed (Syphilis)), hepatitis B surface antigen, or viremic hepatitis C.
- Be currently participating (or participated within the previous 30 days) in an investigational therapy/medication or device trial.
- Be pregnant, nursing, or of childbearing potential while not practicing effective contraceptive methods.
- Any other condition that in the judgment of the Investigator would be a contraindication to enrollment or follow-up.

1. INTRODUCTION

[figure not shown]
1.1 Background

Cardiovascular disease (CVD) is the leading cause of death and disability among people with type 2 diabetes mellitus (DM)¹. Not only are people with DM more likely to have a myocardial infarction (MI), their prognosis is worse, highlighting the need for novel targeted therapies¹. It has long been appreciated that endothelial dysfunction underlies the high rates of CVD associated with long-term DM²⁻⁵. The persistent hyperglycemia and other metabolic abnormalities directly affect the endothelium, contributing to the pathophysiology of disease^{2;6;7}. Numerous cell-based therapy clinical trials in subjects with ischemic heart disease illustrate that mesenchymal stem cell (MSC) administration improves cardiac structure, function and quality of life⁸⁻¹¹. Our recent observation that MSCs improve endothelial progenitor cell (EPC) function (measured by colony forming assay) and endothelial function (measured by brachial artery flow-mediated vasodilation, FMD%) in subjects with ischemic as well as non-ischemic cardiomyopathy¹², independent of their age or DM, suggests that we now have a means to target a primary cause of the CV manifestations of DM. Moreover, the effect on EPCs and FMD% was sustained at 3 months after MSC administration, and evident in subjects receiving allogeneic but not autologous MSCs¹². The mechanisms underlying the therapeutic effects of MSCs are due to a combination of multilineage differentiation, secretion of anti-inflammatory and proangiogenic paracrine factors, as well as stimulation of endogenous progenitor cells growth and differentiation^{12;13}. Moreover, comorbidities and aging are potential factors underlying the difference in efficacy between autologous (subject-derived) and allogeneic (healthy donor) MSCs¹⁴⁻¹⁶.

Endothelial Dysfunction in Subjects with Cardiovascular Diseases

Endothelial dysfunction – defined by impaired flow-mediated vasodilation (FMD) and endothelial progenitor cell (EPC) dysfunction – is a crucial component of the pathophysiology of cardiovascular disease (CVD) and manifests in subjects with cardiovascular risk factors such as atherosclerosis, hypertension, chronic kidney disease, metabolic syndrome, and diabetes mellitus (DM)¹⁷. The endothelium plays an essential role in maintaining circulatory homeostasis by the release of factors that relax and contract vascular smooth muscle, ensuring appropriate blood flow to tissues. As a major regulator of peripheral blood flow, it controls the balance between nitric oxide (NO), reactive oxygen species, vasomotor tone, and inflammation^{18;19}. Any change in the vasomotor regulatory balance may be characterized as endothelial dysfunction that leads to impaired control of vascular tone and participates in the pathogenesis of CVD. By stimulating the release of NO from the endothelium, EPCs play a pivotal part in maintaining vascular homeostasis as well as in mediating vascular repair in damaged endothelium. EPCs regulate the health of the vasculature by incorporating into the endothelium, replacing injured endothelial cells, and secreting angiogenic factors that activate mature endothelial cells²⁰. Subjects with CVD have decreased circulating EPC levels and bioactivity²¹. Indeed, circulating EPC levels serve as a predictor of CV events^{22;23}. Low numbers of EPC-colony forming units (EPC-CFUs) have been linked to

high Framingham risk scores for adverse cardiovascular health outcomes²³. Similarly, brachial reactivity measurements (FMD%) predict long-term cardiovascular events^{24;25}.

Mesenchymal Stem Cells Transplantation for Patients with CVD and Endothelial Dysfunction

The field of cell-based therapy for CVD, particularly ischemic heart disease, has had major advances in the past few years^{2;8-12}. Several studies support the safety and efficacy of MSC based therapy for this large group of subjects who are at major risk for MI, heart failure (HF), sudden cardiac death, and other major CV complications¹⁷⁻²². The DM subject population is at an especially high risk for ischemic heart disease and has a worse prognosis. According to the 2014 National Diabetes Statistics Report, 29.1 million Americans, or 9.3% of the population, had DM in 2012 (mostly type 2). In 2003-2006, CVD death rates were about 1.7 times higher among age-matched adults with DM than among those without DM. Similarly, in 2010 hospitalization rates for MI were 1.8 times higher among adults with DM than among those without DM.

MSCs, under evaluation as a regenerative therapeutic approach for ischemic and non-ischemic cardiomyopathy^{8;9;11;12;26}, have significant potential for clinical benefit in CVD by virtue of their antifibrotic²⁷, anti-inflammatory, and pro-angiogenic properties^{26, 27}, as well as their ability to stimulate endogenous progenitor cells and capacity to differentiate into endothelial cells^{20, 28, 29}. Moreover, there is evidence that NO deficient environments stimulate MSC involvement in angiogenesis^{12;28}. We demonstrated in porcine models of ischemic cardiomyopathy that MSCs reduce infarct size by 35% and significantly improve global and regional left ventricular function^{29;30}. These effects are due to cell engraftment, differentiation into myocytes and blood vessels, and stimulation of endogenous cardiac

stem cell proliferation and differentiation¹³. Given this capacity of MSCs and the role of impaired EPCs in CVD^{31;32}, we tested the hypothesis that MSCs stimulate EPC function and augment vascular relaxation in subjects with heart failure due to idiopathic dilated or ischemic cardiomyopathy¹². We found that allogeneic, but not autologous, MSCs improve EPC bioactivity and endothelial function (FMD%) in heart failure subjects, regardless of etiology. These findings demonstrated a novel clinical beneficial effect of allogeneic MSCs administration in patients with heart failure and have implications for all disorders associated with endothelial dysfunction, such as DM. Notably, DM subjects have impaired EPC mobilization and trafficking from bone marrow as well as functionally impaired MSCs^{33;34}.

Numerous cell-based therapy clinical trials in subjects with ischemic heart disease illustrate that MSC administration improves cardiac structure and function and quality of life⁸⁻¹¹. Our recent observation that MSCs improve EPC function (measured by colony forming assay) and endothelial function (measured by brachial artery flow-mediated dilation, FMD%) in subjects with ischemic as well as non-ischemic cardiomyopathy¹², independent of age or DM, suggests that we now have a means to target a primary cause of the cardiovascular manifestations of DM. Moreover, the effect on EPCs and FMD% was sustained at 3 months after MSC administration, and evident in subjects receiving allogeneic but not autologous MSCs¹². The mechanisms underlying the therapeutic effects of MSCs are due to a combination of multilineage differentiation, secretion of anti-inflammatory and proangiogenic paracrine factors, and stimulation of endogenous progenitor cells growth and differentiation^{12;13}. Moreover, comorbidities and aging are potential factors underlying the difference in efficacy between autologous (subject-derived) and allogeneic (healthy donor) MSCs¹⁴⁻¹⁶.

2. STUDY OBJECTIVES AND ENDPOINTS

2.1 Study Objectives

2.1.1 Primary Objective

- To demonstrate the safety of allogeneic hMSCs administered via infusion therapy for diabetic subjects with endothelial dysfunction.

2.1.2 Secondary Objectives

- To determine the mechanisms underlying the endothelial effects of MSCs and whether targeting endothelial function via MSC therapy ameliorates CVD outcomes in subjects with diabetic mellitus.
- To evaluate the dose and timing of the stimulatory effect of MSCs on circulating angiogenic and inflammatory factor levels and EPC function, as well as FMD%.

2.2 Study Endpoints

2.2.1 Primary Endpoints (Safety)

Safety (Primary): Incidence (at one-month post infusion) of any treatment-emergent serious adverse events (TE-SAEs), defined as the composite of: death, non-fatal pulmonary embolism, stroke, hospitalization for worsening dyspnea and clinically significant laboratory test abnormalities, determined per the Investigator's judgment.

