9.2.4 Subject Stopping Guidelines

This guideline is to be used to indicate boundaries requiring discussion by the Data and Safety Monitoring Board (DSMB) and is designed to assist the independent DSMB in

overseeing the study. The DSMB may also request additional interim analyses and develop other criteria including provision for monitoring of potential late effects to determine when to intervene in the enrollment or treatment of subjects in the study.

The first more conservative stopping guideline is to monitor subjects for unexpected SAEs where there is a reasonable possibility that the study product or administration procedure caused the event within 30 days of administration including cardiorespiratory distress during infusion, subject death, myocardial infarction, hemodynamically unstable ventricular tachycardia, stroke, or more than two related, \geq Grade 3 AEs (based on the NIH CTCAEv4). Study accrual and further treatment of subjects will be put on hold (temporary suspension of study drug administration, pending a safety investigation) if any subjects experience one of these events. The DSMB will be notified within 24 hours of the occurrence of these events and will be convened within 3 business days to review the event and study.

The following are subject stopping guidelines:

- Any subject who develops persistent (that is, still existing more than 3 hours after the end of IP infusion) cardiorespiratory signs or symptoms (for example, shortness of breath, tachypnea, tachycardia, hypotension, or palpitations) will continue with all scheduled follow-up if such follow-up is considered safe in the opinion of the Investigator.
- Any subject whose infusion is stopped due to cardiorespiratory distress will receive no further IP infusions but will continue with all scheduled follow-up if such follow-up is considered safe in the opinion of the Investigator.
- Any subject who develops any sign or symptom that, at the discretion of the Investigator, warrants the discontinuation of infusion will receive no further IP infusions but will continue with all scheduled follow-up if such follow-up is considered safe in the opinion of the Investigator.
- Infusion of the IP may be stopped if there is an adverse event that the Investigator believes is related to the IP or if there is an issue with the IP infusion.

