- The proportion of subjects experiencing TE-SAE as defined in Section 2.2.1 will be monitored within 30 days of injection. This guideline is designed to assist the independent DSMB in overseeing the study and indicate boundaries needing discussion by the DSMB. The DSMB may also request additional interim analyses and develop other criteria including provision for monitoring of potential late effects to determine when to intervene in the enrollment or treatment of subjects in the study.
- The stopping guidelines serve as a mechanism for consultation with the DSMB for additional review, and are not formal “stopping rules” that would mandate automatic closure of study enrollment. It is designed to assist the independent

DSMB in overseeing the study. The DSMB may also request additional interim analyses and develop other criteria including provision for monitoring of potential late effects to determine when to intervene in the enrollment or treatment of subjects in the study.

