9.6 Definition of Serious

An adverse event (AE) or suspected adverse reaction is considered "serious" if it:

1. results in death
2. is life-threatening (at risk of death at the time of the event)
3. requires inpatient hospitalization or prolongation of existing hospitalization

NOTE: Complications that occur during hospitalization are AEs. If a complication prolongs hospitalization or fulfills any other serious criteria, the event is serious. Hospitalization for elective treatment of a pre-existing condition that did not worsen from baseline is not considered to be an AE.

4. results in disability/incapacity

NOTE: *The term disability means a substantial disruption of a person's ability to conduct normal life functions. This definition is not intended to include experiences of relatively minor medical significance such as uncomplicated headache, nausea, vomiting, diarrhea, influenza, accidental trauma (i.e., sprained ankle) that may interfere or prevent everyday life functions but do not constitute a substantial disruption.*

5. Is a congenital anomaly/birth defect.

Important medical events that may not result in death, be life-threatening, or require hospitalization may be considered an SAE when, based upon appropriate medical judgment, they may jeopardize the subject and may require medical or surgical intervention to prevent one of the outcomes listed in the above definition.

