9.15 Regulatory Aspects of Adverse Event Reporting

The Investigator will promptly report all SAEs within the timeframes specified in Section 8.13. Prompt notification of SAEs by the Investigator is essential so that UMMSM can meet legal obligations and fulfill ethical responsibilities towards the safety of all subjects participating in UMMSM-sponsored investigational trials.

The Investigator will comply with the applicable local regulatory requirements related to reporting of SAEs to his or her Institutional Review Board (IRB) or Independent Ethics Committee (IEC).

This protocol has been filed under an Investigational New Drug (IND) application with the FDA. A given SAE may qualify as an Expedited Safety Report (ESR) if the SAE is both at least possibly attributable to study therapy and unexpected. In this case, all Investigators participating in an IND study will receive an ESR.

The ESRs are prepared according to UMMSM policy and are forwarded to the Investigator as necessary. The purpose of the ESR is to fulfill specific regulatory and Good Clinical Practice (GCP) requirements regarding the product under investigation. Based on previous trials involving intravenous infusion of allogeneic human MSCs, no AEs have been attributed to treatment administration; therefore all AEs will be considered and documented as unexpected AEs.

All AEs occurring at any time during the trial will be collected, documented, and reported by the investigator. For each AE, the investigator will provide the date of onset and resolution, intensity, treatment required, outcome, seriousness, and potential causality with regards to the study exposure.

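### The primary endpoint is labelled as any treatment-emergent SAE but defined by five items, so serious events off the list, such as a non-fatal MI, are not counted, and its laboratory item can be read two ways

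*Combined protocol and SAP*

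**What the plan says.** Section 2.2.1 and the synopsis use the same label, "Incidence (at one-month post infusion) of any treatment-emergent serious adverse events (TE-SAEs"), followed by the same definition, "defined as the composite of: death, non-fatal pulmonary embolism, stroke, hospitalization for worsening dyspnea and clinically significant laboratory test abnormalities". The determination is left to the investigator. Neither place says that the list is illustrative.

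Section 9.6 defines serious far more broadly. It covers death, threat to life, disability, congenital anomaly and important medical events, and any event that "requires inpatient hospitalization or prolongation of existing hospitalization", whatever the reason for admission.

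Section 9.2.4 uses two different sets of events:
- Its hold guideline states its aim as follows: "monitor subjects for unexpected SAEs where there is a reasonable possibility that the study product or administration procedure caused the event within 30 days", counted from infusion. The named events include "subject death, myocardial infarction, hemodynamically unstable ventricular tachycardia, stroke, or more than two related" AEs of Grade 3 or above.
- Its monitored quantity is tied to the endpoint: "The proportion of subjects experiencing TE-SAE as defined in Section 2.2.1 will be monitored within 30 days of injection".

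Section 9.15 adds that, because earlier trials attributed no AEs to treatment, "therefore all AEs will be considered and documented as unexpected AEs". It also requires the data that a full SAE count would need: "For each AE, the investigator will provide the date of onset and resolution, intensity, treatment required, outcome, seriousness", along with a causality judgment.

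Sections 9.2 and 9.8 provide for clinically significant laboratory findings to be recorded as AEs, or as SAEs where they qualify. Section 10.2 tabulates AEs by frequency, severity, organ system and relationship; it does not name seriousness. Section 9.10 warns that severe and serious are different things.

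**The concern.** The primary objective is to demonstrate safety, and a reader of the report will take zero TE-SAEs to mean that no subject had a serious event. The definition does not support that. A treated subject could have a related non-fatal MI, the study could be put on hold under Section 9.2.4, and the primary endpoint could still be reported as zero.

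The laboratory item raises a second problem. Two analysts could classify the same investigator-judged abnormality differently, depending on whether they let the word serious in the label govern every item.

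Both problems pass into the proportion that Section 9.2.4 monitors by reference to Section 2.2.1, and into the interim analyses of the primary endpoint mentioned in Section 11.6. Section 10 names no all-SAE incidence that would put the primary result in context.

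**Working it through.** **1. Sections set side by side.** The plan gives no figure to reproduce, so the main check is textual.

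| Event within one month | Serious under 9.6 | Named in the 9.2.4 hold guideline | Counted by the five items |
|---|---|---|---|
| Death (including fatal MI or VT) | Yes | Yes | Yes |
| Non-fatal MI | Yes, by admission, threat to life or medical importance | Yes | No |
| Non-fatal unstable VT | Yes, on the same grounds | Yes | No |
| Unplanned admission not due to dyspnea, PE, stroke or a laboratory abnormality | Yes | No | No |
| Clinically significant laboratory abnormality meeting 9.6 | Yes | No | Yes |
| Clinically significant laboratory abnormality not meeting 9.6 | No | No | Depends on the reading |

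The hold guideline requires an event to be unexpected, reasonably possibly related, and within 30 days. Since Section 9.15 treats every AE as unexpected, relatedness is the condition that decides within that window.

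**2. The two laboratory readings.** Suppose one subject has a non-fatal MI without a laboratory abnormality, and another has a clinically significant but non-serious laboratory abnormality.
- If the item stands as worded, the composite counts 1 subject, the one with the laboratory finding.
- If the label's word serious restricts the item, the composite counts 0.
- The number with any Section 9.6 SAE is 1, the subject with the MI.

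The first reading matches the all-SAE count but identifies a different subject.

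**3. Size for one omitted event (illustration).** Inputs from Section 3.1: pilot 3 + 3 and randomized 5 + 5, so 16 treated, 8 per dose level and 10 randomized. The plan does not specify pooling across phases or doses; Section 10.1 refers only to all randomized subjects. Section 10.2 calls for two-sided 95% intervals without naming a method, so I used exact (Clopper–Pearson) limits:
- 0 of n: upper limit = 1 − 0.025^(1/n). For n = 16 this is 1 − 0.025^(1/16) = 0.206.
- 1 of n: lower limit = 1 − 0.975^(1/n); upper limit = 97.5th percentile of Beta(2, n − 1). For n = 16 these are 0.002 and 0.302.

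| Group | As the composite reports it | With the omitted event |
|---|---|---|
| All treated | 0/16: 0% (0–20.6%) | 1/16: 6.3% (0.2–30.2%) |
| Randomized only | 0/10: 0% (0–30.8%) | 1/10: 10% (0.3–44.5%) |
| One dose level, both phases | 0/8: 0% (0–36.9%) | 1/8: 12.5% (0.3–52.7%) |

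**4. How often this might happen.** The documents give no rate, so this needs an assumption. Let q be the chance that a subject has a serious event off the list and no listed event. The chance of at least one such subject among 16 is 1 − (1 − q)^16: 14.9% for q = 1%, 27.6% for 2%, 56.0% for 5% and 81.5% for 10%.

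**5. Laboratory schedule (separate, lower confidence).** Section 3.1 has safety laboratory tests at every clinic visit except screening. In the text of Table 1 available to me, the hematology and chemistry row has nine cells for ten visits, so one is lost. Wherever that cell belongs, at least three of Days 3, 7, 14 and 28 are unmarked; if the lost cell is blank and falls among those days, all four are. Footnote 3 implies a Day 28 draw, which favors three. The copy has other faults: the infusion mark appears under Day 3, although Section 8.3 places the infusion on Day 0.

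**The case against.** A targeted composite is a legitimate choice for a 16-subject Phase I/II study, and the omitted events are well covered elsewhere. Seriousness is recorded for every AE (Section 9.15), the DSMB Chair is told of each SAE (Section 10.3), AEs and SAEs are summarized semi-annually (Section 11.2), and DSMB reports must contain an SAE summary (Section 11.8). The AE tabulations in Section 10.2 are worded as inclusions, not as a closed set. Sections 9.2.4 and 10.3 say that the guidelines are not formal stopping rules.

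Most of this stands, and it rules out stronger conclusions that a reader might draw:
- **That an MI would go undetected or escape the DSMB.** The sections just cited show otherwise.
- **That non-serious laboratory values definitely count as TE-SAEs.** The items define *serious* adverse events and are left to the investigator's judgment, so the narrower reading is also natural. The text is ambiguous.
- **That the mismatch would change a stopping decision.** No numeric boundary or sample-size calculation in the documents uses the proportion.
- **That the primary endpoint must become any Section 9.6 SAE.** Through the cross-reference in Section 9.2.4 and the abbreviation in the synopsis's pilot-phase check, that would also change the monitored proportion and arguably a condition for treating further subjects.

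The objection does not answer the mismatch itself. A selected composite is defensible, but labelling it as any TE-SAE is not, and good oversight during the trial does not correct the published primary result.

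**Conclusion.** The label and the definition of the primary endpoint contradict each other, and the laboratory item is open to two readings that give different counts. This should be fixed, because with so few subjects a single event separates a zero result from a non-zero one. The damage is confined to the primary result and the proportion monitored under Section 9.2.4.

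The size is illustrative. It assumes one subject with an off-list serious event and no listed event. On the wider laboratory reading, it also assumes that this subject has no clinically significant laboratory value, since such a value would make the subject a primary event.

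Confidence is high on the mismatch, which rests on explicit text. It is lower on the laboratory schedule, and that point does not show that laboratory events would be missed.

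**What to change.** 1. In Section 2.2.1 and the synopsis, name the five-item endpoint a selected composite and drop the word *any*.
2. State there whether a laboratory abnormality must meet Section 9.6 to count.
3. Add to Section 10.2 the number and percentage of subjects with any Section 9.6 SAE with onset from the start of infusion through one month, with an exact 95% CI. Report it beside the composite as the all-SAE incidence, and state the denominator.
4. The sponsor should reconcile which TE-SAE definition applies in the pilot-phase check and in Section 9.2.4. For the pilot check, the synopsis uses the abbreviation, while Section 3.1 speaks of treatment-emergent SAEs without reference to the composite. This review proposes no rule for either place.
5. Separately, reconcile Section 3.1 with Table 1 on the visits at which safety laboratory tests are drawn.

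Items 1 to 3 cost amendment wording and one table line. They need no new data, because seriousness is already recorded for every AE. A small downside is that unrelated admissions may raise the reported all-SAE incidence; Section 10.2 already tabulates relatedness, so this can be shown.
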